In order to better understand treatment mechanisms, and possibly predict long-term outcomes, we propose concurrently to explore Specific Aim 1 (1.1, 1.2, and 1.3) exploratory potential disease biomarkers as outlined below. The primary outcome of this study is motor function rated with the Physical and Neurological Examination for Subtle Signs (PANESS), a validated scale that consistently demonstrates significant impairments in children with ADHD, and which our preliminary data suggest may demonstrate more extreme problems in children with NF1. The first exploratory biomarker is motor system inhibitory physiology, measured using Transcranial Magnetic Stimulation (TMS). Preliminary measures in our NF1 population also show abnormalities similar to established findings in ADHD. The second exploratory biomarker is metabolomics profiling for the biomarker of oligodendrocyte dysfunction in NF1 participants: autotaxin. Preliminary data in our NF1 population showed specific signal abnormalities in the NF1 population compared to healthy controls. Therefore, we propose to perform a double-blind placebo controlled, prospective, Phase IIa study to explore safety, tolerability, and efficacy of NAC on learning and motor behavior in children with NF1 aged 8 through 16 years old.

PURPOSE OF STUDY:

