It has long been known that children with NF1 have enlarged heads – macrocrania. More recent reseach has shown that children and adults with NF1 often have enlarged myelin-rich white matter tracts [6]. These findings have been associated with behavioral and cognitive impairment in NF1 human studies and Nf1 animal models [7] [8]. Oligodendrocytes are the cells that make myelin in white matter tracts. Quantitative biomarkers of white matter structures may help measure and predict behavior in NF1 and facilitate interventions into clinical practice. Diffusion tensor imaging (DTI) shows global changes in NF1 participant brains which are consistent with white matter dysfunction [9]. White matter properties can also be evaluated using neurophysiological techniques, including Transcranial Magnetic Stimulation (TMS). TMS studies are generally brief, inexpensive, readily repeatable, and do not require sedation. TMS may be helpful for identifying clinically useful, specific brain biomarkers and assessments related to motor and learning difficulties in NF1 and, ultimately, other conditions involving RAS pathways (related RASopathies).

The biomarkers in Aim 2 have been developed and optimized in three NIH R01 grants. In collaboration with investigators at the Kennedy Krieger Institute in Baltimore, in studies that are ongoing, we demonstrated in a seminal publication that both the motor control assessment proposed for this study, the PANESS, and the primary physiological biomarker, TMS-evoked Short Interval Cortical Inhibition (SICI), correlate robustly with the presence and severity of ADHD [10]. We and others have also demonstrated that SICI is sensitive to medications, and, further that 4 weeks of treatment with a norepinephrine reuptake inhibitor can both improve ADHD symptoms and, in a statistically correlated way, alter TMS-evoked SICI [11]. In a preliminary study (unpublished data, see figure 2), we have evaluated these potential biomarkers in 11 children with NF1 and compared these to data in approximately 50 children with ADHD and 50 health controls. As shown in figure 2 (NF1 sample n=9 due to age matching), both motor scores with PANESS and TMS-evoked SICI appear to differ in NF1 children, with values as extreme or more extreme than those found in the ADHD cohort. Two other measures are also shown, whose differences were not significant in this study.

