NAC is a natural supplement that acts as an antioxidant and a glutamate modulating agent. It is widely available over the counter. Although no controlled safety studies have been published, NAC has been widely used in large doses for decades in the management of acetaminophen overdose. Its most common side effects are gastrointestinal, as noted in a recent study in children with Autism Spectrum Disorder. Relevant to this proposal, NAC was used to treat ADHD symptoms in systemic lupus erythematosus [17], Autism Spectrum Disorder (ASD), anxiety, and depression [18] [19] with promising responses [15] [16]. Dose of NAC will be used based on these prior published studies. As reported in these studies, there were no serious adverse events. Most side effects, such as nausea, were mild to moderate in severity and were transient and reversible.

Table 1: NAC Preliminary Data							
Condition	Study design	Dose	Sample size	Result	Citation		
SLE with ADHD	Randomized, Placebo	2.4 or 4.8	6 placebo, 9 each	Improved	Garcia 2013 [17]		
	controlled	gm/day	dose; adults, 3 months	ADHD			
Bipolar disorder	Open label	2 gm/day	149 adults, 2 months	Improved	Berk 2011 [20]		
				depression			
Autism Spectrum	12 week double blind	900 mg TID	14 NAC, 15 placebo,	Reduction in	Hardan 2012 [19]		
Disorder	randomized placebo		children	ABC			
	controlled			irritability			

TMS PRELIMINARY DATA: The goal of Aim 2 is to translate molecular, cellular, and animal model data to human NF1 clinical trials through evaluating human brain physiology. Our preliminary work comparing 9 NF1 children (mean IQ 94) with age-matched (all ages 8-12; mean for all groups 10.5 years) cohorts of 52 ADHD and 62 typically developing children (Figures 2a-d) has identified PANESS and TMS-evoked SICI as promising biomarkers.

Version 9.0 MAR2020 Page **6** of **24**

Figure 2. a TMS Resting Motor Threshold (RMT) $(F_{2,113} = 1.7, p = .2)$; **b** Short Interval Cortical Inhibition (SICI) $(F_{2,94} = 10.3, p = .0001)$; **c** Intracortical Facilitation (ICF) $(F_{2,97} = 1.6, p = .2)$; **d** PANESS motor function battery $(F_{2,105} = 30.3, p < .0001)$.

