We will perform serum targeted analysis for LPC, autotaxin activity and LPA measurements pre and post-treatment. We will perform a highly specific mass spectrometry target analysis of LPC species from serum for clinical correlation. We will use authentic standards to accurately measure low and high levels of these biomarkers. This technique will be more reliable and reproducible for clinical applications. We will quantify autotaxin enzyme activity using a fluorometric assay to correlate with LPC measurements (Echelon Biosciences, K-4100). Samples will be collected in EDTA free tubes to avoid interference with analysis per manufacturer recommendations. We will quantify LPA using serum ELISA using the validated kit from Biosource (Reference MBS2024826). In the event that a significant change in autotaxin levels is not observed, we will evaluate untargeted global metabolomics profiling to identify possible disease biomarkers that are affected by NF1 and by treatment with NAC.

9. DATA ANALYSIS/METHODS:

Data Analysis and Data Monitoring-

Data will be maintained on the central servers of Neurology and Human Genetics at Cincinnati Children's Medical Center.

Statistical Analysis:

The purpose of this study is to generate preliminary estimates of effects NAC in NF1 on both behavior and potential biomarkers. Therefore we are not proposing a sample size calculation.

In general, our statistical analysis plan is based upon generalized linear models, particularly linear and logistic regression. The primary dependent variables for Aims 1 and 2 are continuous. For Aim 1, the primary behavioral outcome, which is also the primary outcome for the study, is the Dupaul ADHD rating scale score which rates ADHD behaviors, per the DSM5, in 18 domains, from 0 to 3, for a maximum of 54. Pre and post treatment ADHD will be evaluated with paired t test, with regression analysis to explore additional variables as per below. For Aim 2, PANESS scores and motor evoked potential amplitudes are the primary biomarker measures in the motor system. Analyses of these variables will also be performed pre- and post- treatment with paired t test. These variables will also be correlated, using Pearson or Spearman as appropriate, with the behavioral changes from Aim 1.

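### Section 9 should name the SICI ratio, not motor evoked potential amplitudes, as the Aim 2 TMS measure, and should state a NAC-versus-placebo contrast for it

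*Combined protocol and SAP*

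**What the plan says.** All references are to the combined protocol and SAP.

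For Aim 2, section 9 (Statistical Analysis) states: "PANESS scores and motor evoked potential amplitudes are the primary biomarker measures in the motor system". The next sentence gives the test: "Analyses of these variables will also be performed pre- and post- treatment with paired t test". Section 9 does not say which pulse condition supplies the amplitude, and SICI does not appear in the Statistical Analysis text.

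Other sections identify a different variable:

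- The Background on physiological biomarkers names "the primary physiological biomarker, TMS-evoked Short Interval Cortical Inhibition (SICI").
- TMS Preliminary Data says that the pilot "has identified PANESS and TMS-evoked SICI as promising biomarkers".
- The objective for Aims 1-2 pairs PANESS with SICI as the two measures to compare with existing data.
- The TMS entry in the visit table (Table 2) reads rSICI/fSICI and lists no amplitude.
- Aim 2.1 does not use the word SICI, but its hypothesis is reduced motor cortex inhibition that normalizes on NAC.

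The TMS procedure section defines SICI, in resting muscle, as the mean conditioned response over the mean single-pulse response. On design, the Overview says that each child supplies both control and experimental data. TMS is done at the start and end of each phase (visits 1 to 4).

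**The concern.** Section 9 is where the analysis variable should be fixed, and the variable it names is not the one that the rest of the protocol develops. An analyst who follows it to the letter would test an amplitude, and the inhibition hypothesis of Aim 2.1 would go untested.

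The test has a second gap. A before/after comparison does not by itself separate the effect of NAC from change that would also occur on placebo. The crossover was set up to make that separation, but section 9 does not state the contrast. The trial's stated purpose is to give preliminary effect estimates for potential biomarkers ahead of a larger trial, so the estimate should be of a defined variable and a defined contrast.

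**Working it through.** **1. The plan's own figures.** The upper tail of the F distribution, applied to the Figure 2 caption, gives:

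- SICI, F(2,94) = 10.3: p = 0.00009 (printed .0001)
- ICF, F(2,97) = 1.6: p = 0.21 (printed .2)
- RMT, F(2,113) = 1.7: p = 0.19 (printed .2)

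The printed values reproduce. SICI is the only one of these three TMS measures with a significant group difference, which agrees with the Background: "Two other measures are also shown, whose differences were not significant in this study". This confirms which biomarker the protocol means. It does not size the problem, because no pilot result is given for a raw amplitude.

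**2. What one session yields.** The TMS procedure has three conditions of 20 trials each: single pulse (mean S), 3 ms paired pulse (mean C) and 10 ms paired pulse. By the protocol's definition, SICI = C / S. The 10 ms condition is described as excitatory, so it does not bear on the inhibition hypothesis.

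**3. Each inhibition-related amplitude, read literally.**

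- S: stimulus intensity is chosen so that the response falls in 500-1500 (the unit as printed cancels in the ratio). S is therefore largely a set-up value and carries no information on inhibition.
- C: since C = SICI × S, the value of C depends on where S was set in that session. With SICI unchanged, C can differ between two sessions by a factor of up to 1500 / 500 = 3. This is the outer limit, on the assumption that a session's mean may fall anywhere in the target range. The documents do not say how far sessions really differ.
- C / S: the set-up level is divided out. This is the measure the protocol defines.

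**4. What the pre/post test estimates.** Let τ be the NAC-versus-placebo effect at the end of a phase, and δ the change over a phase that would occur on placebo as well. The mean before/after change on NAC is τ + δ, so a paired t test on it addresses τ + δ. Section 9 does not say which of the four visits form the pair.

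**5. What the crossover can estimate.** Let π1 and π2 be the period effects and d = (visit 2 value) − (visit 4 value).

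- NAC first: mean d = τ + (π1 − π2)
- Placebo first: mean d = −τ + (π1 − π2)
- Half the difference between the two means: [τ + (π1 − π2) + τ − (π1 − π2)] / 2 = τ

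A mixed model on the end-of-phase values, with treatment and period terms and a random child effect, estimates the same τ. Both this and the algebra assume no carry-over from phase I.

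**6. Availability of the data.** TMS is scheduled at weeks 8 and 18. Under the Emergency Study Extension, children then in phase II may have visit 4 TMS late, or omitted if restrictions still hold at week 26. Phase II begins at week 10, so a session just before that cut-off would follow nearly 26 − 10 = 16 weeks of treatment, against 18 − 10 = 8 as planned. The number of children affected is not stated.

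**The case against.** The strongest reply is that the phrase is shorthand. SICI is built from response amplitudes. The objective for Aims 1-2 pairs PANESS with SICI just as section 9 pairs PANESS with amplitudes, and the visit table lists only SICI. This largely stands: the intent is recoverable, and a reader who infers that section 9 deliberately changes the biomarker, or that Aim 2.1 will certainly go untested, goes further than the text allows. Intent stated elsewhere still does not fix the variable in the analysis section.

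A reader might also count intracortical facilitation as a second ratio that the phrase could mean. No section proposes it as the biomarker, so that reading has no support.

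On the test, a reader might infer that placebo data are excluded. They are not. Section 9 does not limit the paired t test to the NAC phase, it provides mixed models for change over time, and it lists treatment assignment among the observed covariates in its discussion of dropout. What stands is narrower: the NAC-versus-placebo contrast is not stated. The same gap affects the other outcomes given the pre/post test, so it is not peculiar to TMS.

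Finally, the TMS aim is exploratory and the plan makes no sample size calculation. That is fair, and it limits the weight of the point.

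**Conclusion.** The point holds as a modest correction. Section 9 names a variable that, read literally, does not test the inhibition hypothesis, and it pairs that variable with a test that states no NAC-versus-placebo contrast. Both conclusions come from comparing the sections and do not depend on assumed values.

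The documents give no size for the consequence. A reader might take one from the pilot by converting F to variance explained: 20.6 / 114.6 = 18% for SICI, against 3.2 / 100.2 = 3% for ICF and 3.4 / 116.4 = 3% for RMT. Those figures should not be used for this purpose. They compare SICI with facilitation and threshold, not with raw amplitude. They come from three-group tests (NF1, ADHD, typically developing) and say nothing about response to NAC. A power comparison would need within-child variances that the documents do not report.

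**What to change.** In section 9:

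1. Replace motor evoked potential amplitudes with the resting SICI ratio: mean 3 ms conditioned MEP divided by mean single-pulse MEP, as defined in the TMS procedure.
2. In place of the pre/post paired t test for this variable, estimate the NAC effect as a within-child NAC-versus-placebo contrast of the end-of-phase values (visits 2 and 4). Use the mixed model that section 9 already allows, with treatment and period terms and a random child effect.
3. State that children whose visit 4 TMS was omitted stay in the model under the missing-at-random assumption that section 9 already makes. Flag delayed visit 4 sessions and repeat the analysis without them.

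Optional clarifications are to define fSICI, which Table 2 lists but the text does not explain, and to name the test for the comparison with healthy controls, for which section 9 gives only the general regression framework.

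The cost is a few sentences. The ratio is already derived in the TMS procedure, the sessions are already scheduled, and no new data are needed.

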The aims of this application are to gain information in children with NF1 about possible clinical benefit of anti-oxidant treatment and to develop and evaluate quantitative brain-based and blood biomarkers relating to presence of NF1, symptom severity, and response to antioxidant therapy. Clinically, 50% of children with NF1 are underperforming or failing at school [1]. This frequently leads to decreased educational attainment and fewer opportunities as adults. An important first step was our preliminary work using the PANESS scale and Transcranial Magnetic Stimulation (TMS)-evoked Short Interval Cortical Inhibition (rSICI) in children with NF1. We propose to develop and extend our understanding of NF1-related motor and learning behavior in response to antioxidant therapy with NAC. The purpose of the present study is to 1) evaluate tolerability, safety, and clinical benefit of NAC in this double-blind placebo controlled study; 2) to evaluate motor function (PANESS) and physiology (TMS) biomarkers at baseline and after treatment; and 3) to quantify metabolomics profiles at baseline and after treatment. We propose to study 20 children with NF1, ages 8-16 years, at baseline and after completion of 8 weeks of treatment with NAC.

NAC therapy, if successful, is expected improve these parameters. Our trial endpoints are: Does behavior improve? Does motor function improve? Are there TMS biomarkers that reflect the presence of NF1 and the response to NAC treatment? Are there metabolomics measures that reflect the presence of NF1 and the response to treatment? We hypothesize that we can identify predictive measures as a foundation for an application for funding for a larger, more definitive, placebo-controlled trial involving biomarkers and clinical outcomes. We believe this work has the potential to lay groundwork for future use of relevant biomarkers for treatment and outcomes research for NF1 as well as other biologically similar conditions, collectively designated the "RASopathies" (due to involvement of the RAS family of proteins) and ultimately to guide development of more effective treatments based on disease pathophysiology.

SPECIFIC AIMS

This study involves the following aims:

Specific Aim 1: Primary Outcome of Study

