For analyses of change over time, mixed models which include subject-specific random effects will be used to account for the correlation of multiple measurements on each subject and capture between-subject variation in rates of change. Unless otherwise noted, the Type I error rate for hypothesis tests and confidence intervals will be controlled at α =0.05. To assist interpretation, the size of effects of interest in each model will be represented by R² (proportion of outcome variation explained by predictors) and/or Cohen's d (difference in group means, in standard deviation units). These effect measures are mathematically related, d=2r/ $\sqrt{(1-r^2)}$. In the case of logistic regression, effect sizes will be given in terms of odds ratios, while predictive accuracy will be assessed using cross-validation procedures.

Exploratory/descriptive data analysis will precede all inferential analyses to ensure that distributional assumptions are satisfied. In addition to computation of basic descriptive sample statistics (measures of central tendency, variability, and bivariate association), graphical tools such as histograms and scatterplots will be used to assess, e.g., approximate normality, linearity, and presence of influential outlying observations. If substantial violations of parametric assumptions are detected, we will implement non-parametric alternatives, including classical rank-based procedures as well as computationally-intensive sample re-use procedures such as the non-parametric bootstrap. Non-parametric procedures generally have

Version 9.0 MAR2020 Page **20** of **24**

less power than parametric procedures when the assumptions of the latter are met, but often have markedly better properties when the assumptions fail.

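### Does the stated conversion between r and Cohen's d inflate the effect sizes from this crossover?

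*Combined protocol and SAP*

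**What the plan says.** Section 9 (Data Analysis/Methods), under Statistical Analysis, says that "the size of effects of interest in each model will be represented by R² (proportion of outcome variation explained by predictors) and/or Cohen's d". It defines the latter as the "difference in group means, in standard deviation units", and then gives the relation between the two: "These effect measures are mathematically related", by d=2r/sqrt(1-r²). The stated use comes at the start of that statement: "To assist interpretation, the size of effects of interest".

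The same section names paired t tests for the ADHD rating scale, PANESS and the TMS measures, and mixed models with subject random effects for change over time. The Overview of Design describes a crossover in which each child supplies data under both treatments.

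On purpose, section 9 says: "The purpose of this study is to generate preliminary estimates of effects NAC in NF1 on both behavior and potential biomarkers". For that reason it gives no sample-size calculation. The Purpose of Study section hopes to find predictive measures "as a foundation for an application for funding for a larger, more definitive, placebo-controlled trial".

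**The concern.** The factor of 2 is usually derived for two independent groups of equal size. Here the main comparisons are within child, and the comparison with existing controls need not be of equal size. The effect-size r that software or a textbook attaches to a paired t test is a partial r: differences between children have been removed from its denominator. Put into the formula, it yields a d well above the difference in SD units, so the two measures given side by side in section 9 would not agree.

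The study offers effect estimates in place of a power calculation and looks ahead to a larger trial. A d that is twice too large, used to plan a parallel-group trial, would cut the sample size about fourfold. It would also overstate the benefit of NAC on a scale that readers use to compare studies.

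**Working it through.** **Inputs.** The formula and the definitions of R² and d come from section 9. The number of children, n = 20, comes from Purpose of Study. The 62 typically developing children come from TMS Preliminary Data. The documents give no within-child correlation (rho), so it is varied over an assumed range of 0 to 0.9.

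**1. The plan's formula under its standard conditions.** For two groups in proportions p and q, r = d/sqrt(d² + 1/(pq)), so d = [1/sqrt(pq)] · r/sqrt(1-r²). With p = q = 0.5 the multiplier is 2. For d = 0.5, r = 0.5/sqrt(0.25 + 4) = 0.2425, and 2(0.2425)/sqrt(1 - 0.0588) = 0.500. Values of 0.2 and 0.8 are also returned exactly.

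**2. Paired data, with R² as section 9 defines it.** Take n scores under each condition from the same children, a mean difference D, and a within-condition SD s.
- Variation explained by condition: 2n(D/2)² = nD²/2.
- Remaining variation: 2(n-1)s².
- R²/(1-R²) = nD²/[4(n-1)s²], so the formula returns (D/s)·sqrt(n/(n-1)).

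Rho does not appear. With D/s = 0.5 and n = 20 the result is 0.5 × sqrt(20/19) = 0.513. A simulation with 200,000 pairs and a true d of 0.5 gave 0.499 to 0.503 at rho = 0.3, 0.5, 0.7, 0.8 and 0.9.

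**3. Paired data, with r taken from the t test.** Here r² = t²/(t² + n-1), and the formula returns 2t/sqrt(n-1). The change-score effect is t/sqrt(n), so the ratio is 2·sqrt(20/19) = 2.05. For a change-score effect of 0.5, t = 0.5 × sqrt(20) = 2.236, r² = 5/(5 + 19) = 0.208, and the formula gives 1.026. The raw-SD effect is the change-score effect times sqrt(2(1-rho)), so inflation against it is 2.052/sqrt(2(1-rho)):

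| Assumed rho | 0 | 0.3 | 0.5 | 0.7 | 0.8 | 0.9 |
|---|---|---|---|---|---|---|
| Formula ÷ raw-SD d | 1.45 | 1.73 | 2.05 | 2.65 | 3.24 | 4.59 |

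**4. Mixed model, with R² that counts the subject effect as explained.** For a true d of 0.5, R² = (0.0625 + rho)/1.0625. The formula gives 1.44, 2.12 and 4.15 at rho = 0.3, 0.5 and 0.8.

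**5. Unequal independent groups.** For 20 against 62 (an assumed pairing, since the plan gives no control count for the main comparison), p = 20/82 and the correct multiplier is 1/sqrt(pq) = 2.33. The formula returns 2/2.33 = 0.86 of the true d, or 0.43 for 0.50. The error here is downward.

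**6. What inflation would cost, if it happened and were used.** For a two-arm trial with 80% power and two-sided 5%, n per arm is about 2(2.80/d)². At d = 0.5 this is 63. At d = 1.026 (step 3, rho = 0.5) it is 15, and 15 per arm has true power of about 28%.

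**The case for a change.** The strongest case for a change is that the sentence covers every model and carries no condition. Steps 3 to 5 show that plausible choices of r or R² move the answer upward or downward, several-fold in some cases. The r from a paired t test is a common one to report. An R² from a regression with several predictors has no single mean difference to convert to. Effect estimates are the main product of the study, and correcting the sentence would cost very little.

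The algebra in that case stands: the formula is not valid for every model, and the plan names neither the R² nor the SD. The consequence does not follow, for three reasons.

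- Inflation needs a partial r, or an R² that includes the subject effect. Section 9 describes R² as the share of outcome variation that the predictors explain. On its natural reading, the share of total variation due to treatment, step 2 applies and the two measures agree.
- Inflation also needs someone to obtain d by conversion. The plan defines d directly from means and SD, allows either measure or both, and mentions the relation only in passing.
- The sample-size loss in step 6 needs the converted d to size a later trial. The stated use is interpretation, and the funding application is to rest on predictive measures. Section 9 also promises summary statistics of location, spread and bivariate association, which are what a planner would need to work from means, SDs and the within-child correlation.

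**Conclusion.** The concern does not call for a change. Read as written, the plan gives a sound d: 0.51 for a true 0.50 with 20 complete pairs, the small excess being the factor sqrt(20/19). The figures of 2.05 times, and of 1.45 to 4.6 times, are correct only for a calculation that the plan does not describe, and the wider range rests on an assumed rho. In a comparison with a larger control group, a converted d would be too small (ratio 0.86 at an assumed 20 against 62).

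The remaining gap is one of detail: the condition of equal-sized conditions with r from total variation is not stated, and the standardising SD is not named. In a 20-child exploratory study, an analyst who computes d from the observed means and reports the SD used fills that gap, and no planned test or estimate changes. The conclusion assumes that R² means the share of total outcome variation and that d is computed from its stated definition.
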